3.2.2 Safety Variables

Safety and general tolerability of the IMP variables include:

- Treatment-Emergent Adverse Event (TEAEs)
- Physical examinations including body weight at screening, day 3 and final visit/ETV.
- Vital signs at screening, day 1 (pre and post dose), day 3 (post dose), day 6 (pre and post dose) and Final visit (post dose)/ETV.
- 12-lead ECG at screening.

- Laboratory tests at screening, day 3 and the final visit/ETV:
 - Haematology:
Leukocytes and leukocyte differential count (percentage values and absolute values), erythrocytes, haemoglobin (conv. units), haemoglobin (IS units), haematocrit, MCV, MCH, MCHC, thrombocytes.
 - Blood chemistry:
Electrolytes: sodium, potassium, calcium, chloride, inorganic phosphorus
Enzymes: alkaline phosphatase, γ -GT, AST, ALT.
Substrates/metabolites: total bilirubin, creatinine, glucose, BUN or urea, uric acid, total cholesterol, triglycerides.
Proteins: total proteins.
 - Urine analysis:
Urine chemical analysis: pH, specific gravity, appearance, colour, nitrites, proteins, glucose, urobilinogen, bilirubin, ketones, blood, leukocytes, erythrocytes, epithelial, crystals, cylinders.

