4.10.2 Clinical Laboratory Evaluation

Laboratory values (hematology, biochemistry, and urinalysis) will be listed by subject and study time point including changes from baseline for continuous variables. The baseline for the laboratory values will be the results obtained on the last measurement before the first dose.

All values outside the clinical reference ranges will be flagged in the data listings. The abnormal values will be flagged with 'L' for values below the lower limit of the clinical reference range and 'H' for values above the upper limit of the clinical reference range and included in the listings. The Investigator will assess whether the values outside the clinical reference range are clinically significant and these will be reported as "abnormal, not clinically significant (NCS)" or "abnormal, clinically significant (CS)". Clinically significant laboratory values will be recorded by the Investigator as AEs.

Quantitative laboratory assessment reported as "<X", i.e. BQL, or ">X", i.e. above the upper limit of quantification, will be converted to X for the purpose of quantitative summaries, but will be presented as recorded, i.e. as "<X" or ">X" in the listings.

The toxicity grading of laboratory tests is determined based on the NCI CTCAE V4.03 ([Appendix 3](#)).

The following summaries will be provided for laboratory data:

- Absolute value and change from baseline for continuous data by scheduled time point.
- The number and percentage of subjects in each test result category for categorical data, by scheduled time point.
- Shifting from baseline of subjects with lab results evaluation as Normal, NCS, and CS, by scheduled time point.
- Shifting from baseline of subjects with lab results evaluated by NCI CTCAE V4.03 by toxicity grading and scheduled time point.

The following laboratory data listings will be provided:

- Listing of laboratory test results
- Listing of abnormal laboratory test results
- Listing of other lab tests and pregnancy tests.

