APPENDIX 3 CTC Grading for Laboratory Parameters

Laboratory measurements will be graded using the NCI-CTCAE v4.03.

		Grade						
Analytic		Direction	Unit	0	1	2	3	4
	Hematology							
Hemoglobin	Hypo	g/L	LLN <= Value	100 <= Value < LLN	80 <= Value < 100	Value < 80		
	Hypo	g/dL	LLN <= Value	10 <= Value < LLN	8 <= Value < 10	Value < 8		
	Hypo	mmol/L	LLN <= Value	6.2 <= Value < LLN	4.9 <= Value < 6.2	Value < 4.9		
WBC	Hypo	10^9/L	LLN <= Value	3 <= Value < LLN	2 <= Value < 3	1 <= Value < 2	Value < 1	
	Hypo	/mm3	LLN <= Value	3000 <= Value < LLN	2000 <= Value < 3000	1000 <= Value < 2000	Value < 1000	
Neutrophils	Hypo	10^9/L	LLN <= Value	1.5 <= Value < LLN	1 <= Value < 1.5	0.5 <= Value < 1	Value < 0.5	
	Hypo	/mm3	LLN <= Value	1500 <= Value < LLN	1000 <= Value < 1500	500 <= Value < 1000	Value < 500	
Lymphocytes	Hypo	10^9/L	LLN <= Value	0.8 <= Value < LLN	0.5 <= Value < 0.8	0.2 <= Value < 0.5	Value < 0.2	
	Hypo	/mm3	LLN <= Value	800 <= Value < LLN	500 <= Value < 800	200 <= Value < 500	Value < 200	
	Hyper	10^9/L	Value <= ULC		4 < Value <= 20	20 < Value		
	Hyper	/mm3	Value <= ULN		4000 < Value <= 20,000	20,000 < Value		
Monocytes		NA						
Eosinophils		NA						
Basophils		NA						
Platelet count	Hypo	10^9/L	LLN <= Value	75 <= Value < LLN	50 <= Value < 75	25 <= Value < 50	Value < 25	
	Hypo	/mm3	LLN <= Value	75,000 <= Value < LLN	50,000 <= Value < 75,000	25,000 <= Value < 50,000	Value < 25,000	
	Biochemistry							
Serum creatinine		Hyper	umol/L	Value <= ULN	ULN < Value <= 1.5 < ULN	1.5 < ULN < Value <= 3 < ULN	3 < ULN < Value <= 6 < ULN	6 < ULN < Value
BUN		NA						
Alanine aminotransferase (ALT)		Hyper	U/L	Value <= ULN	ULN < Value <= 3 < ULN	3 < ULN < Value <= 5 < ULN	5 < ULN < Value <= 30 < ULN	20 < ULN < Value
Aspartate aminotransferase (AST)		Hyper	U/L	Value <= ULN	ULN < Value <= 3 < ULN	3 < ULN < Value <= 5 < ULN	5 < ULN < Value <= 30 < ULN	20 < ULN < Value
Alkaline phosphatase (ALP)		Hyper	U/L	Value <= ULN	ULN < Value <= 2.5 < ULN	2.5 < ULN < Value <= 5 < ULN	5 < ULN < Value <= 20 < ULN	20 < ULN < Value
Total bilirubin		Hyper	umol/L	Value <= ULN	ULN < Value <= 1.5 < ULN	1.5 < ULN < Value <= 3 < ULN	3 < ULN < Value <= 10 < ULN	10 < ULN < Value
Albumin		Hypo	g/L	LLN <= Value	30 <= Value < LLN	20 <= Value < 30	Value < 20	

		Grade						
Analytic		Direction	Unit	0	1	2	3	4
Sodium	Hypo	g/dL	LLN <= Value	3 <= Value < LLN	2 <= Value < 3	Value < 2		
			LLN <= Value	130 <= Value < LLN		120 <= Value < 130	Value < 120	

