	Hyper	mmol/L	LLN <= Value	ULN < Value <= 150	150 < Value <= 155	155 < Value <= 160	160 < Value	
Potassium	Hypo	mmol/L	LLN <= Value	3 <= Value < LLN		2.5 <= Value < 3	Value < 2.5	
	Hyper	mmol/L	Value <= ULN	ULN < Value <= 5.5	5.5 < Value <= 6	6 < Value <= 7	7 < Value	
Chloride		NA						
	Serology							
HBV		NA						
HCV		NA						
	Urinalysis							
Urine protein	Hyper		Negative	1+	2+			
	Hyper	g/24hrs	Value <= ULN	ULN < Value < 1	1 <= Value < 3.4	3.5 < Value		
	Pregnancy test							
Pregnancy test		NA						

LLN: lower limit of normal; ULN: upper limit of normal.

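### SAP Appendix 3, sodium Hyper row as printed: Grade 0 has no upper limit, so a sodium above ULN fits two grades (confirm the cell in the source file first)

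*SAP*

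**What the plan says.** Appendix 3 opens with "Laboratory measurements will be graded using the NCI-CTCAE v4.03" and then tabulates limits by analyte, direction, unit and grade. The row in question prints "Hyper mmol/L LLN <= Value ULN < Value <= 150", followed by Grade 2 from above 150 to 155, Grade 3 from above 155 to 160, and Grade 4 above 160 mmol/L. It carries no analyte name of its own. Its mmol/L limits and its place directly before potassium identify it as sodium.

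The potassium row just below, in the same direction and unit, prints "Hyper mmol/L Value <= ULN ULN < Value <= 5.5". There Grade 0 stops at ULN.

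SAP 4.10.2 uses these grades for one planned summary: "Shifting from baseline of subjects with lab results evaluated by NCI CTCAE V4.03 by toxicity grading and scheduled time point". Sodium is among the analytes in SAP 3.2.2, which schedules "Laboratory tests at screening, day 3 and the final visit/ETV".

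**The concern.** Grades for one analyte in one direction should not overlap. In this row they do: the Grade 0 condition is the one the table otherwise uses for low-direction (Hypo) rows, and it does nothing to exclude high values.

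The SAP does not say which grade wins. Neither Appendix 3 nor SAP 4.10.2 has a rule that the highest matching grade applies. The worst-case rules in SAP 4.10.1 concern adverse event severity and causality, not laboratory grades.

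The result would then depend on the order of the programmer's tests. Code that tests Grade 0 first would give every high sodium Grade 0, and the table would show no upward sodium shift. Code that tests from Grade 4 downwards would grade the same values correctly. Two programmers working from the same SAP could produce different tables.

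**Working it through.** The plan gives no figure to reproduce here. The check is whether the printed conditions give one grade per value.

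**Inputs**
- From SAP Appendix 3, with v the sodium value in mmol/L: Grade 0 is v ≥ LLN; Grade 1 is ULN < v ≤ 150; Grade 2 is 150 < v ≤ 155; Grade 3 is 155 < v ≤ 160; Grade 4 is v > 160.
- The table footnote defines LLN and ULN as the lower and upper limits of normal, so LLN < ULN.
- The documents give no numeric limits for sodium. The pairs below are assumptions.

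**Logic**
1. If v > ULN, then v > LLN, so Grade 0 is met.
2. For ULN below 150, Grades 1 to 4 together cover every v > ULN, so exactly one of them is also met.
3. Every value above ULN therefore meets two grades, whatever the limits are.
4. If v < LLN, no condition in this row is met.

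**Numerical check**
Sodium from 110 to 170 mmol/L in steps of 0.5 gives 121 values. The row was applied as printed, then with Grade 0 changed to v ≤ ULN.

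| Assumed LLN / ULN | Values above ULN | Meeting two grades, as printed | Values below LLN | Meeting no grade, as printed | Values not meeting exactly one grade, Grade 0 capped at ULN |
|---|---|---|---|---|---|
| 130.5 / 143 | 54 | 54 | 41 | 41 | 0 |
| 135 / 145 | 50 | 50 | 50 | 50 | 0 |
| 137 / 147 | 46 | 46 | 54 | 54 | 0 |
| 136 / 149 | 42 | 42 | 52 | 52 | 0 |

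With 135 / 145, a sodium of 146 meets Grades 0 and 1, 152 meets 0 and 2, 158 meets 0 and 3, and 165 meets 0 and 4. With Grade 0 capped at ULN they meet only 1, 2, 3 and 4 respectively.

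**Comparison within the table**
Creatinine, ALT, AST, alkaline phosphatase, total bilirubin and potassium all give Grade 0 in the high direction as a value not above ULN. Sodium is the one chemistry Hyper row of seven that does not.

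**Results that use the row**
A shift table uses the baseline grade as well as the later ones. With 24 subjects and three scheduled tests (screening, Day 3, final visit), that is 24 × 3 = 72 results, of which 24 × 2 = 48 are post-baseline. This assumes full attendance and no unscheduled tests.

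**The case against.** The strongest objection is that the cell may not be real. The text was read from a PDF, and this part of the table is visibly broken. The row just above the affected block prints "Sodium Hypo g/dL LLN <= Value 3 <= Value < LLN", yet its g/dL limits of 3 and 2 are those of the albumin g/L row (30 and 20) divided by ten. The row after it, with limits 130 and 120, has lost its analyte, direction and unit. A Grade 0 cell carried over from a neighbour cannot be excluded, and coding the printed text cannot show what the source file says.

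This lowers confidence and makes a source check the first step. It does not remove the point. The visible damage is to labels, directions and units, while the grade cells around it remain coherent. The row itself has a direction, a unit and five grade cells. A slip in the source is also plausible: version 3.1 in the SAP revision history says ULC was changed to ULN in this appendix, yet one lymphocyte cell still reads ULC.

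The second objection is that the intent is clear. CTCAE v4.03 is the named standard, and Grade 1 in the same row starts above ULN. The revision history also mentions a separate ADaM specification, so the code may be right. That stands, and it is why the code should be checked before anything is rerun.

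A reader might go further and infer that the ALT and AST rows overlap too, since Grade 3 prints as "5 < ULN < Value <= 30 < ULN" while Grade 4 starts above 20. Those cells show the multiplication sign misread as a less-than sign, so single characters there cannot be relied on. A reader might also suspect the potassium row, but it would overlap only if the site's ULN exceeded 5.5 mmol/L, and no document gives that limit. Neither is part of this point.

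**Conclusion.** The point holds as a minor one, with medium confidence. As printed, every sodium above ULN meets Grade 0 and one of Grades 1 to 4, and the SAP has no rule to choose between them. This does not depend on the assumed limits. It does depend on the cell reading the same in the source file.

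The effect is confined to the sodium part of one descriptive safety table. The documents give no basis for estimating how many of the 72 results exceed ULN. High values would still be visible elsewhere under SAP 4.10.2: the H flags, the change-from-baseline summaries, the listing of abnormal results, and the separate summary "Shifting from baseline of subjects with lab results evaluation as Normal, NCS, and CS, by scheduled time point". The pharmacokinetic analysis is untouched.

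A reader might infer that the sodium shift table was produced wrongly or that high sodium values were hidden. The documents do not support that. They show no output, and harm would require the cell to be real, the code to have copied it, and Grade 0 to have been tested first.

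**What to change.** 1. Check the sodium Hyper Grade 0 cell in the SAP source file. If it already stops at ULN, no change is needed.
2. If it reads as printed, change it to a value not above ULN, matching the other six chemistry Hyper rows.
3. Check that the grading code uses that rule.
4. Rerun the sodium part of the CTCAE shift table only if the code followed the printed cell.
5. Record the correction in the SAP Addendum, which SAP section 1 provides for changes after database lock.

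The cost is one cell, one code check and, at most, a rerun of part of one table. No data collection or other analysis changes.
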